Potential subjects will be recruited from a pool of TKA patients presenting to Cleveland Clinic orthopedic providers at main campus that may benefit from using a knee brace.. This study aims to complete follow-up with 40 patients. 20 out of 40 patients will receive adjunct therapy using the OCSI brace. Patients will be allocated to one of these two groups via computer randomization. The PI ([name]) will be blinded to patient compliance and evaluation during data acquisition and statistical analysis. All study patients will receive standard of care therapy (pain medications, and other modalities as needed). At home physical therapy will occur at standard of care scheduled intervals. Once physical therapy begins at Cleveland Clinic, patients in both the control and brace group will receive outpatient Physical Therapy 2 times a week for two weeks, then the number of physical therapy visits will be at the discretion of the clinician.

Patient selection:

- Age: 50 or older

- Radiographic: Varus or valgus knee deformity less than 10 degrees
- BMI of 40 or less

Research Procedures

Visit 0: Potential patients will be consented during their office visit with [name]. Once consented, patients will be computer randomized into either the knee brace group or the control group. For the knee brace group, measurements will be taken during the clinic visit, an order will be written for the brace and sent to Hanger Clinic where they will be in contact with the study participant to schedule the brace fitting. The subject can start wearing the brace at this time until surgery.

Visit 1 (6 weeks prior to surgery): Participant will meet with study coordinator and complete both questionnaires and physical tests.

Visit 2 (1 week prior to surgery): Participant will meet with study coordinator and complete both questionnaires and physical tests.

Visit 3 (1 week after surgery): Participant will meet with study coordinator and complete both questionnaires and physical tests. The brace will NOT be worn until after staple removal (10 to 14 days after surgery).

Visit 4 (6 weeks after surgery): Participant will meet with study coordinator and complete both questionnaires and physical tests.

Visit 5 (12 weeks after surgery): Patient will meet with study coordinator and complete both questionnaires and physical tests. At this point, the study time points are complete and the brace no longer needs to be worn for the study.

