Descriptive statistics (mean, standard deviation, and coefficient of variation) will be used to compare the demographics between the two cohorts. Functional metrics will be compared pre- and post-surgery at 0- and 3- months. Unless otherwise indicated, all testing of statistical significance will be two-sided, and a difference resulting in a p-value of less than or equal to 0.05 will be considered statistically significant. Also, after each analysis, General Linear Models (GLM) will be used to control for possible confounders, including BMI, gender, age, and ethnicity.

Adverse Events and Data Monitoring Committee

Procedural safety will be documented in this study through patient and surgeon reported adverse events. ARs will be documented for all ceases in this study.

An unanticipated problem involving risks to participants or others is any event that (1) is unforeseen, (2) caused harm or placed a person at increased risk of harm, and (3) is related to the research procedures.

An Adverse Event (AE) is any untoward or unfavorable medical occurrence, including any abnormal sign (for example, abnormal physical exam or laboratory finding), symptoms, or disease. Adverse events can encompass both physical and psychological harms.

An Internal Adverse Event (AE) is an untoward medical occurrence, which occurs to participants in research conducted by Cleveland Clinic and/or Cleveland Clinic is the IRB of record.

External Adverse Event (AE) is an untoward medical occurrence experienced by subjects enrolled at other institutions for the same study approved at Cleveland Clinic or a different study using the same study drug/device.

A Serious Adverse Event (SAE) is any adverse experience that results in any of the following outcomes:

- Death

- A life-threatening experience
- Inpatient hospitalization or prolongation of existing hospitalization
- A persistent or significant disability/incapacity
- A congenital anomaly/birth defect
- Important medical events that may not result in death, be life-threatening, or require hospitalization may be considered a serious adverse experience when, based upon appropriate medical judgment, they may jeopardize the patient or subject and may require medical or surgical intervention to prevent one of the outcomes listed in this definition.

An Unexpected Adverse Event means any AE not previously known or included in the consent form or other risk information.

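### The adjusted model names four demographics but not the patient's own baseline value of the outcome, so with 20 per arm the plan forgoes a likely gain in precision

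*Combined protocol and SAP*

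**What the plan says.** The Sample section sets the size: "This study aims to complete follow-up with 40 patients", and "20 out of 40 patients will receive adjunct therapy using the OCSI brace".

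The Data Analysis section gives two elements. The main comparison is "Functional metrics will be compared pre- and post-surgery at 0- and 3- months". It does not say which visit is month 0, whether change scores are meant, or how the two arms are compared. The second element comes on top of the first, being run once each analysis is done: "General Linear Models (GLM) will be used to control for possible confounders, including BMI, gender, age, and ethnicity". Those four are given as examples, so the list is open. No baseline value of any outcome is named.

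The schedule table places every functional test, knee score, patient-reported score and pain score at two pre-operative visits, about 6 weeks and 1 week before surgery. For the first of these, Research Procedures says "Visit 1 (6 weeks prior to surgery): Participant will meet with study coordinator and complete both questionnaires and physical tests". Randomisation comes earlier, at Visit 0, where the brace is also ordered. Of the brace group the protocol says "The subject can start wearing the brace at this time until surgery".

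**The concern.** In a randomised comparison, covariates serve to reduce residual variance and to correct chance imbalance. They do so only as far as they predict the outcome. For a timed walking or stair test, or a knee score, the natural predictor is the same patient's result on the same measure before surgery. The plan collects that result but does not put it in the model. It names general demographics instead, one of which (ethnicity) may take several degrees of freedom out of 38.

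With 40 patients, precision is scarce. A chance difference in starting function between two groups of 20 would be only partly corrected by age, gender, BMI and ethnicity. Because the model is not written down, the analyst could also choose between change scores, follow-up values and different covariate sets after seeing the data.

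**Working it through.** **The plan's own figure.** The plan states 40 patients, 20 per arm, without an effect size, SD, power or pre/post correlation. The number therefore cannot be reproduced.

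**Inputs from the documents.** N = 40, 20 per arm; two-sided 0.05 ("all testing of statistical significance will be two-sided, and a difference resulting in a p-value of less than or equal to 0.05"); covariates BMI, gender, age and ethnicity.

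**Assumptions (not in the documents).** True difference d = 0.8 SD; correlation r between the pre-operative and 3-month values from 0.3 to 0.7; share of variance explained by the demographics (R²) from 0 to 30%; ethnicity coded with 1 to 4 degrees of freedom, so k = 4 to 7 covariate df in all.

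**Step 1: no adjustment.** SE = √(2/20) = 0.316 SD. Noncentrality is 0.8/0.316 = 2.53 on 38 df, which gives power of 69%.

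**Step 2: the named covariates.** Expected variance relative to no adjustment is (1 − R²) × 37/(37 − k). Setting this to 1 gives break-even R² = k/37:

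| k | break-even R² | SE ratio if R² = 0 |
|---|---|---|
| 4 | 4/37 = 10.8% | √(37/33) = 1.059 |
| 6 | 6/37 = 16.2% | √(37/31) = 1.092 |
| 7 | 7/37 = 18.9% | √(37/30) = 1.111 |

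With k = 4, the SE ratio is 1.03 at R² = 5%, 1.005 at 10%, 0.95 at 20% and 0.89 at 30%. The effect can go either way. If the covariates explain nothing, the SE is about 6% wider (k = 4) to 11% wider (k = 7).

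**Step 3: baseline as covariate, compared with change scores.** The variance ratios are:
- baseline alone: (1 − r²) × 37/36;
- baseline plus three demographics that explain nothing further: (1 − r²) × 37/33;
- change score: 2(1 − r), assuming equal SDs before and after surgery.

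Power at d = 0.8, from the noncentral t:

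| r | baseline alone | baseline + 3 uninformative demographics | change score |
|---|---|---|---|
| 0.4 | 76% | 72% | 61% |
| 0.5 | 80% | 76% | 69% |
| 0.6 | 86% | 83% | 79% |
| 0.7 | 93% | 90% | 89% |

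**Step 4: size in patients.** At r = 0.5 the variance ratio for baseline alone is 0.75 × 37/36 = 0.771. Its inverse is 1.30, so the gain is worth about 30% more patients than no adjustment. At r = 0.3 the ratio is 0.91 × 37/36 = 0.935, a saving of about 6%. With three uninformative demographics added it becomes 0.91 × 37/33 = 1.02, and the gain is gone.

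**Simulation check.** In 8,000 simulated trials per setting, the SE was 0.314 unadjusted, 0.335 with four uninformative covariates and 0.278 with a baseline of r = 0.5. The formulas give 0.316, 0.316 × 1.059 = 0.335 and 0.316 × 0.878 = 0.278.

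**The case against.** Four arguments can be made for leaving the text alone.

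1. *The list is open and the GLM is a follow-up analysis.* This is true: the baseline value is not excluded, and the GLM does not replace the main comparison. But an open list leaves the choice until after the data are seen. The fair criticism is that the model is under-specified, not that baseline adjustment is ruled out.

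2. *The pre/post comparison may already use the patient's own earlier value through change scores.* This is possible, and the text does not settle it. At r = 0.5 a change score has the same power as no adjustment, and below that it has less. At r = 0.7 it comes close to ANCOVA. Within the range examined it never does better than baseline alone.

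3. *The remedy may cost what it criticises.* This stands in part. Each uninformative demographic kept beside the baseline takes back some of the gain, and at r = 0.3 three of them cancel it. Extra covariates should therefore be optional and few.

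4. *There is no clean baseline.* This is the strongest argument, and it stands against the present schedule. All tests follow randomisation, the first has a window of ±4 weeks, and the brace may be worn before it. Since the objective covers function before as well as after surgery, adjusting for a value that the brace has already changed would remove part of the effect under study. The plan's own pre/post comparison has the same weakness, so leaving the text as it is does not avoid the problem. The timing of the first test has to be part of the fix.

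**Conclusion.** The concern holds as one of under-specification and forgone efficiency. The plan names no baseline outcome value as a covariate and does not define a baseline-adjusted comparison of the arms. It also schedules no functional test before randomisation. At an assumed d of 0.8 SD and r of 0.5, using the baseline alone would raise power from 69% to 80%. The gain is small at r = 0.3 and large at r = 0.7, and the documents give no correlation to choose between these.

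Two stronger readings are tempting. A reader might infer that the planned GLM loses precision. The documents do not show this: a loss occurs only if the covariates explain less than about 11% to 19% of the variance, depending on how ethnicity is coded, and nothing in the plan fixes that share. Leaving out the baseline forgoes a gain; it does not itself cause a loss. A reader might also state the gain against the planned GLM, where it looks larger: with k = 6 and R² = 10% the ratio is 1.074/0.771 = 1.39. That figure rests on two further assumptions, so the 30% against no adjustment is the safer one.

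The plan is not invalid on this account. The change should be made before any outcome data are analysed.

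**What to change.** Replace the GLM sentence in Data Analysis with wording such as: 'For each functional, patient-reported and pain outcome, the arms will be compared at 3 months by ANCOVA with the first pre-operative value of that outcome as covariate. Any further demographic covariates are listed here and will not be changed. Ethnicity will be reported descriptively.'

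In Research Procedures and the schedule table, place that first set of tests at Visit 0 before randomisation or, failing that, before any brace wear. Do not use the test one week before surgery as the covariate, since the brace group may have been wearing the brace by then.

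If some patients are nevertheless first tested after brace wear has begun, report how many, and give the comparison without baseline adjustment in all randomised patients as the sensitivity analysis. Do not drop those patients: they can come only from the brace arm, and removing them would break the randomised comparison.

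The cost is one sentence of analysis text and a change in the order of the first test session relative to randomisation or fitting. No new outcome measure is needed.

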Chart review: At 9 months, the study team will review participant’s chart for pain medication utilization and number of physical therapy visits during the study.

	Visit 0 Office visit (scheduling surgery)	Visit 1 6 weeks prior to surgery (±4 weeks)	Visit 2 1 week prior to surgery (±1 week)	Visit 2 1 week after surgery (±1 week)	Visit 3 6 weeks after surgery (±2 weeks)	Visit 4 12 weeks after surgery (±2 weeks)	9 months After surgery (chart review)
Informed Consent	X						
Randomization	X						

Timed up and go (TUG) test		X	X	X	X	X	
Timed stair-climb test		X	X	X	X	X	
Single-limb stance time (bilateral)		X	X	X	X	X	
6 minute walk test		X	X	X	X	X	
AROM, PROM		X	X	X	X	X	
Knee Society objective score		X	X	X	X	X	
Knee Society functional Score		X	X	X	X	X	
KOOS (Jr)		X	X	X	X	X	
HSS scale		X	X	X	X	X	
Pain score on visual analog scale (rest)		X	X	X	X	X	
Pain score on visual analog scale (activity)		X	X	X	X	X	
Pain medications utilization		X	X	X	X	X	X
Number of therapy visits							X

- For this research study, we will ask you to fill out some additional physical tests will be performed. These tests include:
 - Timed up and go (TUG) test: standing up from seated position and walking to a designated line, walking back, and returning to seated position
 - Timed stair-climb test: walking up and down stairs
 - Single-limb stance time (bilateral): standing on one leg unassisted

- 6 minute walk test: distance walked in 6 minutes
- Patient reported outcomes will also be assessed using multiple validated questionnaires
 - Knee Society Score (KSS)
 - Knee Injury and Osteoarthritis Outcome Score (KOOS Jr)
 - HSS scale
 - Visual Analog Scale (Pain score)

Participant Compliance

Study participants will be given a pedometer and notebook supplied by the sponsor to record daily steps. This will be used to monitor compliance with physical therapy and the use of the brace as it is expected there should be increased activity over time.

Data Analysis

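### Adverse events have no scheduled enquiry at study visits or in the 9-month chart review, so complications may be under-counted and possibly reported differently by arm

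*Combined protocol and SAP*

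**What the plan says.** The section Adverse Events and Data Monitoring Committee names two sources: "Procedural safety will be documented in this study through patient and surgeon reported adverse events". It adds "ARs will be documented for all ceases in this study", which I read as adverse events and cases. It gives no form, question, timing or collection window. The rest of the section defines event types and sets deadlines for reporting to the IRB, which run from the time an event becomes known.

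Under Research Procedures, the four visits at 6 weeks and 1 week before surgery and at 1 and 6 weeks after it carry the same description: "Participant will meet with study coordinator and complete both questionnaires and physical tests". The 12-week visit has the same content and then closes the schedule: "At this point, the study time points are complete and the brace no longer needs to be worn for the study". The schedule table has rows for physical tests, scores, pain and pain medication, but none for adverse events. The notebook described under Participant Compliance is for daily steps.

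At 9 months, "the study team will review participant’s chart for pain medication utilization and number of physical therapy visits during the study". No complication, readmission or reoperation is listed.

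The brace is worn in two periods. Before surgery, after the fitting is arranged: "The subject can start wearing the brace at this time until surgery". After surgery: "The brace will NOT be worn until after staple removal (10 to 14 days after surgery"), and then until the 12-week visit.

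**The concern.** The plan says in detail what happens once an event is known, but little about how events come to be known. Unprompted reports depend on the patient thinking an event worth mentioning and on the surgeon hearing of it. Events managed by other clinicians, and those after the last visit, are the most exposed. At 9 months the study team opens the chart, where many such events would be recorded, but extracts other items.

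The plan's own safety rules depend on counts. The internal-event rule covers events occurring more often or more severely than expected, and the IRB reads the summary log for trends in frequency and severity. Counts from unprompted reports are a weak basis for either.

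The comparison is with standard of care without a sham brace, so patients know their arm. The brace arm alone has a contact with the orthotics clinic. Both facts make differential reporting possible. With 20 patients per arm, one or two events missed or gained would change the picture.

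**Working it through.** The plan states no adverse-event rate or capture rate, so there is no figure to reproduce. The check has four parts.

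**1. Where an event could be picked up by design**

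| Occasion | Stated content | Adverse-event enquiry stated? |
|---|---|---|
| Five coordinator visits | Questionnaires and physical tests; pain medication in the schedule | No |
| 9-month chart review | Pain medication, number of therapy visits | No |
| Patient or surgeon report | Adverse events, all cases | Yes, but no timing or method |
| IRB reporting rules | Apply after discovery | Not a means of finding events |

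**2. Time between study contacts**

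Inputs: brace restart at day 10 to 14 (Research Procedures); 6-week visit ±2 weeks, so day 28 to 56; 12-week visit ±2 weeks; chart review at 9 months (schedule). Assumption: 9 months = 9 × 52/12 = 39 weeks.

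- Restart to the 6-week visit, nominal: 42 − 14 = 28 to 42 − 10 = 32 days.
- Across the window: 28 − 14 = 14 to 56 − 10 = 46 days.
- The first post-operative visit is at 1 week ±1 week, so up to day 14. It can coincide with or follow staple removal, and in that case the first contact after restart comes sooner.
- Last visit to chart review: 39 − 12 = 27 weeks, and 27/39 = 69%. With the last visit at week 14, 25/39 = 64%; at week 10, 29/39 = 74%.

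These are intervals between scheduled research contacts. They do not measure lost events.

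**3. What incomplete capture would do (illustration; risk and capture are assumed)**

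Let p be the true risk per patient, s the share of events recorded, and n = 20 per arm. Expected recorded events = 20ps. Chance of recording at least one = 1 − (1 − ps)^20.

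| p | Expected, s = 1 | Expected, s = 0.6 | At least one, s = 1 | At least one, s = 0.6 |
|---|---|---|---|---|
| 5% | 1.0 | 0.6 | 64% | 46% |
| 10% | 2.0 | 1.2 | 88% | 71% |
| 20% | 4.0 | 2.4 | 99% | 92% |

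With no true difference, the apparent brace/control ratio is s(brace)/s(control):

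- 60%/60% gives 1.0
- 80%/70% gives 1.14
- 90%/60% gives 1.5
- 60%/90% gives 0.67

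Any inequality comes entirely from the assumed capture difference, and it can go either way.

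**4. What 20 patients can show with full capture**

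For 0 events in 20, the exact upper limit is 1 − 0.025^(1/20) = 16.8% (two-sided 95%), or 1 − 0.05^(1/20) = 13.9% (one-sided 95%).

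**The case against.** The best defence is that events are not ignored. Patients and surgeons are named sources, all cases are to be documented, and no end date is set for surgeon reports. Patients meet the coordinator five times for range of motion, pain and Knee Society scores, and the adverse-event definition includes abnormal examination findings. Staple removal and physical therapy add clinical contact in both arms. An operating surgeon could well know of a manipulation, infection or reoperation. Weeks after the 12-week visit are not brace weeks, and the wording of the chart review may confine it to the study period. The text as read also has a break in the schedule after the randomisation row, so a lost row cannot be fully excluded, though the visit text and the chart-review sentence agree with the table.

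Much of this stands, and it rules out three stronger readings that a reader might infer.

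- **That events will be counted unequally by arm.** Study visits are identical in both arms. The brace-only fitting is arranged before surgery, and the orthotist is not a named reporter. Unmasked allocation makes unequal reporting possible but does not establish it.
- **That nothing is collected at visits, or for 69% of follow-up.** The documents show that no enquiry is scheduled. They do not show that volunteered events go unrecorded or that surgeon reporting stops.
- **That the trial will wrongly declare the brace safe.** The plan states no safety objective and no comparison of events by arm.

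What survives is narrower: capture depends on unprompted reports, no route from therapists to the adverse-event record is stated, and the chart is opened without extracting complications.

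**Conclusion.** The point holds as a limited, inexpensive improvement. The plan has no scheduled or systematic adverse-event enquiry at its five coordinator visits, and complications are not among the items taken from the chart at 9 months. Complications during brace wear and after week 12 may be under-counted and, in an unmasked comparison, possibly reported differently by arm. About 27 of 39 post-operative weeks (69%, or 64% with the last visit at week 14) have no scheduled study contact. That figure rests on taking 9 months as 39 weeks. The extent of under-counting cannot be derived from the documents, and the capture figures above only illustrate how sensitive small counts are. Better capture would make the counts more complete, but 20 patients per arm could still not support a conclusion of safety.

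**What to change.** 1. In the existing 9-month chart review, add readmission, emergency visit, wound complication or infection, thromboembolism, fall, manipulation and reoperation, each with its date. Do this for all randomised patients, on the same form in both arms, and abstract without knowledge of arm where feasible. The brace order may reveal the arm in the chart, so masking may be only partial. State that the review covers the whole period up to 9 months.
2. Add an adverse-event row to the schedule. At each existing pre- and post-operative visit the coordinator asks the same short fixed checklist in both arms. Identify visits by timing, because the visit text numbers them 1 to 5 and the schedule numbers them 1, 2, 2, 3, 4.
3. In Data Analysis, report counts by arm descriptively with exact confidence intervals, and state that no conclusion of safety will be drawn from them.

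The cost is a few minutes per visit and modest extra abstraction time; no new visit is needed. Events treated elsewhere and absent from the chart may still be missed. Dated readmissions and reoperations would also serve the plan's cost goal.
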